#### Physical Examination Findings

Physical examinations will be conducted at all clinic visits and findings will be recorded as normal, abnormal but not clinically significant, and abnormal and clinically significant. Abnormal changes in baseline physical examinations findings will be summarized using counts and percentages of patients in the Safety Population. Abnormal findings noted at baseline will be listed for each patient. Any changes in physical examination findings at post-baseline visits relative to the previous visit will be listed.

#### Neurological Examination Findings

Neurological examinations will be conducted at all clinic visits and will include evaluation of cranial nerves, motor function, sensory function, reflexes and coordination/cerebellar function. Findings will be recorded as normal, abnormal but not clinically significant, and abnormal and clinically significant. The number and percentage of patients with abnormal neurological findings will be summarized by parameter. Abnormal neurological findings at baseline will be listed for each patient. Any changes in neurological findings at post-baseline visits relative to the previous visit will be listed.

#### Developmental Examination Findings

Developmental examinations will be conducted on pediatric patients 2 to 17 years of age, inclusive. Developmental parameters assessed include speech and language skills, motor skills and social skills with findings recorded as normal, abnormal but not clinically significant, and abnormal and clinically significant. The number and percentage of pediatric patients with abnormal developmental findings will be summarized by parameter. Abnormal developmental findings at baseline and any changes in neurological findings at post-baseline visits relative to the previous visit will be listed for each patient.

#### **4.3.4.      Electrocardiogram (ECG)**

Safety ECG measurements will be collected throughout the study. Baseline ECG values are those collected at Visit 1, the first visit of the OLE prior to the first dose of IP.

ECG parameters include heart rate, PR interval, RR interval, QRS interval, QT (uncorrected) interval, QTcF interval, and QTcB interval. In addition, the overall

interpretation of the investigator will be documented as normal, abnormal but not clinically significant (NCS), or abnormal and clinically significant (CS). All clinically significant abnormal findings will be reported as AEs also. Absolute values and change from baseline in post-baseline values will be summarized. By-patient listings of ECG data and overall interpretations will be provided.

#### 4.3.5. Columbia-Suicide Severity Rating Scale (C-SSRS)

The Columbia-Suicide Severity Rating Scale (C-SSRS) is a patient questionnaire that evaluates suicidal ideation and behaviors. The results (yes/no) from the 5 questions under suicidal ideation and the 5 questions under suicidal behavior will be summarized at baseline and post baseline using percentages and counts. The denominator for percentages will be the number of subjects with a C-SSRS assessment at baseline or at any time post baseline. The post-baseline by-question summary will list a subject as "yes" if they selected yes at any time after baseline.

The C-SSRS suicidal behavior and suicidal ideation scores recorded at baseline and any changes in post-baseline scores from the previous visit will be summarized descriptively by visit, including the number and percentage of subjects reporting any suicidal behavior and any suicidal ideation as defined in **Table 1**. Adult and pediatric C-SSRS data will be summarized separately.

C-SSRS data collected, including scores for suicidal ideation, intensity of ideation and actual suicide attempts, will be listed by patient and visit.

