### 1.3 Schedule of Activities

**Table 1. Schedule of Activities for Open-Label Phase**

Week (All dates are relative to the first OLE dose on Day 1)	0	Open-Label Maintenance												Safety Follow-up	
		Year 1				Year 2				Year 3 b					
		13	26	39	52	65	78	91	104	117	130	143	156		
Visit and Visit Windows (Telehealth permitted where it is accepted as the standard of care)	First Visit of the OLE a V1	All windows for these visits are $\pm$ 14 days												$\pm$ 3 days	
		V2 Phone	V3	V4 Phone	V5	V6 Phone	V7	V8 Phone	V9	V10 Phone	V11	V12 Phone	V13 or ET c		
Screening and Diagnosis															
Informed Consent/Assent	X														
Inclusion/Exclusion Criteria	X														
Demographics and Medical History Review d	X														
Safety Assessments															
Vital signs (BP, HR, RR, body temperature, height, weight)	X		X		X		X		X		X		X	X	
Physical/Neurological/Developmental Examination	X		X		X		X		X		X		X	X	
12-lead ECG	X		X											X	
Clinical Laboratory Tests e	X		X		X		X		X		X		X		
Pregnancy Test (and dispense pregnancy test for monthly home testing; WOCBP) f	X														
Investigational Product PK g	X		X		X										
Concomitant ASM Level Review (if collected per standard of care) h	X		X		X		X		X		X		X		
Adverse Events	X	X	X	X	X	X	X	X	X	X	X	X	X	X	
Concomitant Medication Review	X	X	X	X	X	X	X	X	X	X	X	X	X	X	
C-SSRS (since previous visit) i	X		X		X		X		X		X		X	X	

Week (All dates are relative to the first OLE dose on Day 1)	0	Open-Label Maintenance											Safety Follow-up
		Year 1				Year 2				Year 3 b			
		13	26	39	52	65	78	91	104	117	130	143	156
Visit and Visit Windows (Telehealth permitted where it is accepted as the standard of care)	First Visit of the OLE a V1	All windows for these visits are $\pm$ 14 days											$\pm$ 3 days
		V2 Phone	V3	V4 Phone	V5	V6 Phone	V7	V8 Phone	V9	V10 Phone	V11	V12 Phone	V13 or ET c
Efficacy Assessments													
Seizure eDiary review	X	X	X	X	X								
CGI-CSID	X		X		X		X		X		X		X
CGI-I by parents/ caregiver(s)/LAR(s) and clinician	X		X		X		X		X		X		X
SF-36	X		X		X								
Investigational Product													
Dispense IP	X		X		X		X		X		X		X

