## 5.2 Exclusion Criteria

1. Pregnant or breastfeeding.
2. An active CNS infection, demyelinating disease, or degenerative neurological disease.
3. History of psychogenic nonepileptic seizures.
4. Any disease or condition (other than TSC) at the initial visit that could compromise the hematologic, cardiovascular (including any cardiac conduction defect), pulmonary, renal, gastrointestinal, or hepatic systems; or other conditions that might interfere with the absorption, distribution, metabolism, or excretion of the IP, or would place the participant at increased risk or interfere with the assessment of safety/efficacy. This may include any illness in the past 4 weeks which in the opinion of the investigator may affect seizure frequency.
5. Unwillingness to avoid excessive alcohol use or cannabis use throughout the study.
6. Have active suicidal plan/intent or have had active suicidal thoughts in the past 6 months or a suicide attempt in the past 6 months.
7. Known sensitivity or allergy to any component in the IP(s), progesterone, or other related steroid compounds.
8. Exposed to any other investigational drug (except for GNX in Study 1042-TSC-2001 or Study 1042-TSC-3001) or investigational device within 30 days or fewer than 5 half-lives prior to Visit 1 (first visit of the OLE). For therapies in which half-life cannot be readily established, the Sponsor’s medical monitor should be consulted.

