### **2.3. Study Endpoints**

#### **2.3.1. Primary Endpoint**

The primary endpoints are the following safety endpoints:

- Incidence and severity of AEs, SAEs and withdrawals and dose-reductions due to AEs

- Vital sign measurements including blood pressure, heart rate, respiratory rate, body temperature, height, and body weight
- Physical, neurological, and developmental examination
- 12-lead ECG
- Clinical laboratory tests
- C-SSRS.

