### **2.3.2. Secondary Endpoints**

The secondary endpoints are:

- Percentage change from baseline in 28-day seizure frequency during open-label treatment (first year only)
- Number (%) of participants considered treatment responders (first year only)
- CGI-I at the last scheduled study visit
- Change from baseline in the quality-of-life scale SF-36 (first year only)
- Change from baseline in the percentage of seizure-free days during treatment, based on seizure type (first year only)
- Change from baseline of CGI-CSID

Note that original baseline in 28-day seizure frequency in the parent study will be applied. For other assessments, the baseline is considered to be Visit 1, the first visit of the OLE.

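### No planned C-SSRS table counts participants whose suicidal ideation or behavior is new or worse than at OLE Visit 1, and from Week 52 the change score cannot stand in for that count

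*SAP*

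**What the plan says.** SAP 2.3.1 introduces its list with "The primary endpoints are the following safety endpoints", and C-SSRS is the last item. SAP 4.3.5 plans three kinds of output.

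- **By question.** Yes/no results at baseline and post-baseline. A participant is a post-baseline yes "if they selected yes at any time after baseline". The baseline answer plays no part. The denominator rule is: "The denominator for percentages will be the number of subjects with a C-SSRS assessment at baseline or at any time post baseline".
- **By visit.** Baseline scores are summarized, and "any changes in post-baseline scores from the previous visit will be summarized descriptively by visit". The same summary also carries prevalence counts, described as "including the number and percentage of subjects reporting any suicidal behavior and any suicidal ideation".
- **Listings** by patient and visit.

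Adult and pediatric data are summarized separately. SAP Table 1 only groups items into behavior, ideation and self-injury. It does not define new-onset or worsened suicidality.

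The SAP's baseline note in 2.3.2 reads: "For other assessments, the baseline is considered to be Visit 1, the first visit of the OLE". In the protocol's Schedule of Activities the instrument appears as "C-SSRS (since previous visit)", at Visits 1, 3, 5, 7, 9, 11, 13 and 14. Protocol 8.3.5 has each assessment after Visit 1 compared with the visit before it.

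**The concern.** Protocol 8.3.5 says that ganaxolone is related to products with a raised risk of suicidal ideation or behavior. The natural question for this endpoint is therefore how many participants developed ideation or behavior that they did not have at Visit 1, or had it more severely than then.

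Elsewhere the SAP is built to answer that kind of question. Laboratory values get change from baseline and a shift table from baseline class to worst post-baseline class (4.3.2). Vital signs and ECG get change from baseline (4.3.3, 4.3.4). A TEAE must start or worsen on or after the first dosing day (4.3.1). C-SSRS has no counterpart: its change score is tied to the previous visit, and its ever-yes count mixes carry-over from Visit 1 with new onset. At stake is whether the clinical study report can state a count of new or worsened cases without someone compiling it by hand from listings that run over three years.

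**Working it through.** The plan gives no figure to reproduce; the study is descriptive and unpowered (SAP 3.1, 3.2). The check is what each planned summary shows for a given course. Assumption: the ideation score runs 0 to 5, the highest of the five ideation items in SAP Table 1 answered yes, with 0 for none.

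**Single courses (Visit 1, then Weeks 26, 52, 78)**

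| Course | Change from previous visit | Change from Visit 1 | Ever yes | New or worse |
|---|---|---|---|---|
| 0-3-3-3 | +3, 0, 0 | +3, +3, +3 | yes | yes |
| 0-1-2-3 | +1, +1, +1 | +1, +2, +3 | yes | yes |
| 4-2-3-2 | -2, +1, -1 | -2, -1, -2 | yes | no |
| 2-2-2-2 | 0, 0, 0 | 0, 0, 0 | yes | no |

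At Week 26 the two change columns agree, because Visit 1 is the previous C-SSRS visit. They part from Week 52.

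**Group illustration (assumed).** 10 of 100 participants go from 0 to 3 at Week 26 and stay there. Mean change at Week 26 is 10 × 3 / 100 = +0.3 on either reference. At Week 156 it is 0 against the previous visit and +0.3 against Visit 1. The by-visit count of any ideation shows 10% at every post-baseline visit, so the cases can be seen, but as prevalence. The use of a mean is an assumption; SAP 4.3.5 says only that the summary is descriptive.

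**All possible courses.** Four visits with six levels give 6^4 = 1296 courses. They are unweighted: this shows logic, not trial frequencies.

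- Never above Visit 1: 1³ + 2³ + 3³ + 4³ + 5³ + 6³ = 441. Above it at some visit: 1296 − 441 = 855. All 855 contain at least one visit-to-visit increase.
- Of the 441, 126 never increase between visits, so 441 − 126 = 315 show an increase without ever exceeding Visit 1.
- Of the 441, 6 have only zeros after Visit 1, so 441 − 6 = 435 are an ever-yes without new onset or worsening.
- Second and third post-baseline visits with a score above Visit 1: 1080. Of these, 420 (39%) show a change of zero or less from the previous visit.

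**Allowing for exclusion criterion 6.** Protocol 5.2 excludes participants who "Have active suicidal plan/intent or have had active suicidal thoughts in the past 6 months" or an attempt in that time. It does not name a wish to be dead, the first ideation item in SAP Table 1. If Visit 1 scores can then be only 0 or 1, there are 2 × 6³ = 432 courses. Those that never exceed Visit 1 number 1³ + 2³ = 9. Of these, 4 show an increase (for example 1-0-1-0) and 7 are an ever-yes. Later visits above Visit 1 number 648, of which 300 (46%) show a change of zero or less. So the criterion nearly removes the carry-over and relapse problems, but does nothing for persistent worsening in the change score.

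**What can be recovered from the planned tables.** For one item, among participants assessed both at Visit 1 and later, let B be the number positive at Visit 1 and E the number ever positive later. New onset lies between E − B and E. It is known exactly only if B = 0, and the bound needs the same participants in both counts, which the denominator rule does not secure. It also says nothing about worsening within ideation.

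**The case against.** The strongest reply is that the planned outputs together show more than the change score alone. The by-visit counts keep a persistent case visible at every visit. Every course that worsens produces at least one visit-to-visit increase. Criterion 6 makes active ideation at Visit 1 rare, so ever-yes is close to new onset on those items. Individual courses can be read from the listings, and clinically significant worsening in a safety assessment is also an adverse event (Protocol 10.4.1), tabulated as a TEAE. All of this stands, and it limits the harm. None of it supplies a count of participants who are new or worse than at Visit 1.

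The previous-visit reference also comes from the protocol. Protocol 8.3.5 and the form named in the Schedule of Activities both use it, and SAP 4.3.3 lists examination changes in the same way. A reader might infer that the SAP contradicts the protocol here; it does not. But visit-to-visit comparison serves monitoring, and nothing in the protocol prevents a baseline-referenced summary.

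A reader might also infer that the tables hide persistent suicidality. The by-visit counts rule that out. Or a reader might say that ever-yes rises artificially because Visit 1 covers a short look-back while follow-up runs to about Week 160. That accumulation is real, but the documents give no event rate or look-back length to size it, and a new-onset count over the same follow-up accumulates just as much. It is not an argument for the change proposed here.

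**Conclusion.** The point holds as a gap in the summary of a listed primary endpoint. From Week 52 the change score shows zero for worsening that persists, and can show an increase for a participant who never exceeds Visit 1. The ever-yes count does not separate carry-over from new onset. No table sets a participant's worst post-baseline category against his or her own Visit 1 category.

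The size cannot be given as a frequency, because the documents contain no C-SSRS rates. The course counts and the +0.3 example are logical illustrations resting on the 0 to 5 scoring assumption. The endpoint is not made uninterpretable: prevalence by visit remains valid, and Week 26 is unaffected. Visit 1 is also not an untreated baseline, since participants arrive on ganaxolone, and there is no control arm. New or worse than Visit 1 therefore describes what emerged during the extension and does not isolate a drug effect.

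**What to change.** In SAP 4.3.5:

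1. Summarize score change from baseline (Visit 1). Keep the previous-visit comparison of Protocol 8.3.5 for visit-level monitoring and the listings.
2. Keep the by-visit counts of any ideation and any behavior.
3. Add, separately for adult and pediatric data, a shift table of Visit 1 category (none / ideation / behavior) by worst post-baseline category, among participants with both assessments.
4. Report n (%) with new-onset ideation or behavior among those without it at Visit 1, and n (%) whose maximum post-baseline ideation score exceeds their Visit 1 score.
5. State that these counts are descriptive.

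An axis for the worst category before the OLE is optional, and only if parent-study C-SSRS data are integrated; the documents do not describe such integration.

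Cost: revised SAP wording and one extra table per age form. Visit 1 and all later C-SSRS assessments are already scheduled, so no assessment is added.

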**Table 1: C-SSRS Categories for Analysis**

Category	C-SSRS Item response is "YES"
Suicidal behavior	Preparatory acts or behavior Aborted attempt Interrupted attempt Actual attempt Complete suicide
Suicidal ideation	Wish to be dead Non-specific active suicidal thoughts Active suicidal ideation with any methods (not plan) without intent to act Active suicidal ideation with some intent to act, without specific plan Active suicidal ideation with specific plan and intent
Non-suicidal self-injurious behavior	Non-suicidal self-injurious behavior

## 4.4. Statistical Methods for Secondary Efficacy Analyses

### 4.4.1. Percentage change from baseline in 28-day seizure frequency during open-label treatment.

Seizure types are defined as the following: focal motor seizures without impairment of consciousness or awareness, focal seizures with impairment of consciousness or awareness with motor features, focal seizures evolving to bilateral, tonic-clonic convulsive seizures, and generalized motor seizures including tonic-clonic, bilateral tonic, bilateral clonic, or atonic/drop seizures. Seizures must have a motor component sufficiently prominent and distinct to clearly establish the observed symptoms as epileptic in origin. Seizures that do not count towards the efficacy endpoints include: focal aware seizures without motor features (eg, absence or focal nonmotor seizures with or without impairment of awareness), infantile or epileptic spasms, and myoclonic seizures.

Baseline for efficacy assessments is defined as based on the participant's prior study as follows:

- Study 1042-TSC-2001 – the original 4-week screening period for participants continuing in Study 1042 TSC-3002
- Study 1042-TSC-3001 – the original 4-week screening period for participants previously randomized to GNX.

Post-baseline 28-day seizure frequency will be calculated as the total number of seizures in the open-label phase divided by the number of days with seizure data in the same period, multiplied by 28. Baseline 28-day seizure frequency will be calculated as the total number of seizures in the baseline phase divided by the number of days with seizure data in the same period, multiplied by 28. The calculation for percent change from baseline in 28-day seizure frequency will be done as follows for each participant:

$$\left( \frac{[(\text{Post-baseline 28-day seizure frequency}) - (\text{Baseline 28-day seizure frequency})]}{(\text{Baseline 28-day seizure frequency})} \right) \times 100\%$$

The baseline, post-baseline, and arithmetic and percent changes from baseline in 28-day seizure frequency will be summarized using descriptive statistics. The following subgroup summarizations will be also applied:

- Gender (Female vs Male).
- Age groups (1 to 6 years; 7 to 12 years; 13 to 17 years; and 18 years and above).

#### **4.4.2. Number (%) of participants considered treatment responders**

The number and percentage of subjects experiencing a reduction (improvement) of at least 50% from baseline in the 28-day seizure frequency of the primary seizure types will be summarized. In addition, a cumulative responder curve figure will be provided, in which the X-axis represents amount of improvement in increments of 5%, and the Y-axis represents the percentage of subjects improving by at least the amount on the X-axis. The treatment groups will be presented separately within the figure. Subgroup summaries for gender and age groups listed in section 4.4.1 will be also applied.

#### **4.4.3. CGI-I at the last scheduled study visit**

The CGI-I is 7-point scale, and the number and percentage of subjects with each score will be summarized. The scores range from 1=very much improved and 7=very much worse. The CGI-I is completed by both parent/caregiver/LAR and clinician.

#### **4.4.4. Change from baseline in the quality-of-life scale SF-36**

The SF-36 is a multi-purpose survey designed to capture participant or parent/caregiver perceptions of own health and well-being. The SF-36 has 36 items grouped in 8 dimensions: physical functioning, physical and emotional limitations, social functioning, bodily pain, general, and mental health.

Scoring the 36-Item Health Survey is a two-step process. First, precoded numeric values are recoded per the scoring key given in

**Table 2.** Note that all items are scored so that a high score defines a more favorable health state. In addition, each item is scored on a 0 to 100 range so that the lowest and highest possible scores are 0 and 100, respectively. Scores represent the percentage of total possible score achieved. In step 2, items in the same scale are averaged together to create the 8 scale scores.

**Table 3** lists the items averaged together to create each scale. Items that are left blank (missing data) are not considered when calculating the scale scores. Hence, scale scores represent the average for all items in the scale that the respondent answered.

**Table 2: Recoding Items for SF-36**

Item numbers	Change original response category	To recoded value of:
1, 2, 20, 22, 34, 36	1 →	100
	2 →	75
	3 →	50
	4 →	25
	5 →	0
3, 4, 5, 6, 7, 8, 9, 10, 11, 12	1 →	0
	2 →	50
	3 →	100
13, 14, 15, 16, 17, 18, 19	1 →	0
	2 →	100
21, 23, 26, 27, 30	1 →	100
	2 →	80
	3 →	60
	4 →	40
	5 →	20
	6 →	0
24, 25, 28, 29, 31	1 →	0
	2 →	20
	3 →	40
	4 →	60
	5 →	80
	6 →	100
32, 33, 35	1 →	0
	2 →	25
	3 →	50
	4 →	75
	5 →	100

**Table 3: Averaging Items to Form Scales for SF-36**

Scale	Number of items	After recoding per Table 1, average the following items
Physical functioning	10	3 4 5 6 7 8 9 10 11 12
Role limitations due to physical health	4	13 14 15 16
Role limitations due to emotional problems	3	17 18 19
Energy/fatigue	4	23 27 29 31
Emotional well-being	5	24 25 26 28 30
Social functioning	2	20 32
Pain	2	21 22
General health	5	1 33 34 35 36

#### **4.4.5. Change from baseline in the percentage of seizure-free days during treatment, based on seizure type**

The percentages of seizure-free days will be based on the primary seizure types. Post-baseline percentage of seizure-free days will be calculated as the number of days in the open-label treatment phase with zero seizures divided by the number of days with seizure data in the phase, multiplied by 100. The baseline percentage of seizure-free days will be calculated as the number of days in the 4-week baseline phase with zero seizures divided by the number of days with seizure data in the baseline phase, multiplied by 100.

The baseline and post-baseline values and the arithmetic changes from baseline will be summarized using descriptive statistics.

